3.3.4.2 Withdrawal of consent to trial participation

Subjects may withdraw their consent to trial participation at any time without the need to justify the decision. If a subject wants to withdraw consent, the investigator should be involved in the discussion with the subject and explain the difference between trial treatment discontinuation and withdrawal of consent to trial participation, as well as explain the options for continued follow up after trial treatment discontinuation, please see Section 3.3.4.1 above.

3.3.4.3 Discontinuation of the trial by the sponsor

Boehringer Ingelheim reserves the right to discontinue the trial at any time for any of the following reasons:

1. New toxicological findings, serious adverse events, or any safety information invalidating the earlier positive benefit-risk-assessment. More specifically, the trial will be terminated if more than 50% of the subjects have drug-related and clinically relevant adverse events

of moderate or severe intensity, or if at least 1 drug-related serious adverse event is reported

2. Violation of GCP, or the CTP impairing the appropriate conduct of the trial
3. The sponsor decides to discontinue the further development of the investigational product

3.3.5 Replacement of subjects

In case more than 3 subjects do not complete the trial, the Clinical Trial Leader together with the Trial Pharmacokineticist and the Trial Statistician are to decide, if and how many subjects will be replaced. A replacement subject will be assigned a unique trial subject number.

4. TREATMENTS

4.1 INVESTIGATIONAL TREATMENTS

BI 730357 will be provided by BI Pharma GmbH & Co. KG, Germany. Rosuvastatin, digoxin, metformin and furosemide will be obtained from a public pharmacy.

4.1.1 Identity of the Investigational Medicinal Products

The characteristics of the trial products are given below:

Trial product 1

Name: * CRESTOR[®] 10 mg Film-coated tablet
Substance: Rosuvastatin (as rosuvastatin calcium)
Pharmaceutical formulation: Film-coated tablet
Holder of marketing authorization: [REDACTED]
Unit strength: 10 mg
Posology: 1 – 0 – 0 (cocktail component)
Route of administration: Oral
Duration of use: single dose on Day 1 of visit 2 and 3

Trial product 2

Name: * Lenoxin[®] 0,25 mg tablets
Substance: Digoxin
Pharmaceutical formulation: Tablet
Holder or marketing authorization: [REDACTED]
Unit strength: 0.25 mg
Posology: 1 – 0 – 0 (cocktail component)
Route of administration: Oral
Duration of use: single dose on Day 1 of visit 2 and 3

Trial product 3

Name: * MetfoLiquid GeriaSan[®] 1000 mg/5 ml oral solution
Substance: Metformin hydrochloride
Pharmaceutical formulation: Oral solution
Holder of marketing authorization: [REDACTED]
Co-marketing: [REDACTED]
Unit strength: 1000 mg/5 mL
Posology: 0.05 mL (10 mg) – 0 – 0 (cocktail component)
Route of administration: Oral
Duration of use: single dose on Day 1 of visit 2 and 3

Trial product 4

Name: * Lasix[®] liquidum 10 mg/ml oral solution
Substance: Furosemide (as furosemide sodium)
Pharmaceutical formulation: Oral solution
Holder of marketing authorization: [REDACTED]
Unit strength: 10 mg/mL
Posology: 0.1 mL (1 mg) – 0 – 0 (cocktail component)
Route of administration: Oral
Duration of use: single dose on Day 1 of visit 2 and 3

* These trial products may be replaced by generics which will be announced via a non-substantial CTP amendment.

Trial product 5

Substance: BI 730357
Pharmaceutical formulation: Film-coated tablet
Source: BI Pharma GmbH & Co. KG, Germany
Unit strength: 100 mg
Posology: 3 – 0 – 3
Route of administration: Oral
Duration of use: from Day -7 to Day 6 of Visit 3 (13 days in total)

4.1.2 Selection of doses in the trial

[REDACTED]
[REDACTED] 0.25 mg digoxin, 1 mg furosemide, 10 mg metformin hydrochloride and 10 mg rosuvastatin (see Section 1, Introduction).

4.1.3 Method of assigning subjects to treatment groups

There is only one treatment sequence investigated in this trial, and each subject will be allocated to the same treatment sequence (R-T). The subjects will be allocated to a study subject number by drawing lots prior to first administration of trial medication in the morning of Day 1 of Visit 2.

Once a subject number has been assigned, it cannot be reassigned to any other subject.

4.1.4 Drug assignment and administration of doses for each subject

This trial is a non-randomised 2-period fixed-sequence study. All subjects will receive the two treatments in a fixed sequence (Reference always followed by Test). The treatments to be evaluated are outlined in Table 4.1.4: 1 below.

[figure not shown]
Table 4.1.4: 1 Dosage and treatment schedule

Treatment	Substance	Formulation	Unit strength	Dosage	Total daily dose
R (cocktail)	Digoxin	Tablet	0.25 mg	1 tablet as single dose	0.25 mg
	Furosemide	Oral solution	10 mg/mL	0.1 mL (1 mg) as single dose	1 mg
	Metformin	Oral solution	1000 mg/5mL	0.05 mL (10 mg) as single dose	10 mg
	Rosuvastatin	Film-coated tablet	10 mg	1 tablet as single dose	10 mg
T	BI 730357	Film-coated tablet	100 mg	3 tablets (300 mg) bid for 13 days on Day 1 the morning dose is given 1 h prior to the cocktail	600 mg
	Digoxin	Tablet	0.25 mg	1 tablet as single dose	0.25 mg
	Furosemide	Oral solution	10 mg/mL	0.1 mL (1 mg) as single dose	1 mg
	Metformin	Oral solution	1000 mg/5mL	0.05 mL (10 mg) as single dose	10 mg
	Rosuvastatin	Film-coated tablet	10 mg	1 tablet as single dose	10 mg

The investigator (or authorised designee) will administer the trial medication as an oral dose together with about 240 mL of water (BI 730357) or 280 ml (for the cocktail) to subjects who are in standing position. For drug administration, the so-called four-eye principle (two-person rule) should be applied. For this, one authorised employee of the trial site should witness the administration of trial medication, and – if applicable – its preparation (e.g. reconstitution), if correct dosage cannot be ensured otherwise.

Fed conditions

A standardized meal (bread roll with butter, cheese and/or sliced sausage) will be served 30 min before each BI 730357 administration. The subjects must completely consume the meal prior to drug intake. To assure comparable conditions for the cocktail administration, the standardised meal will be served also in the Reference treatment 90 min prior to the planned dosing of the cocktail (the meal is to be consumed within 30 min).

Thereafter, complete drug administration is assumed.

All components of the cocktail should be administered within 2 minutes.

After cocktail administration (in R and T)

Subjects will be kept under close medical surveillance until 48 h following cocktail administration. During the first 4 h after cocktail administration, they are not allowed to lie down (i.e. no declination of the upper body of more than 45 degrees from upright posture), unless required for medical procedures. For restrictions with regard to diet, see Section [4.2.2.2](#).

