4.2.2.2 Restrictions on diet and life style

While admitted to the trial site, the subjects are restricted from consuming any other foods or drinks than those provided by the staff. Standardised meals will be served at the time points described in the [Flow Chart](#). No food is allowed for at least 4 h after intake of the cocktail.

On Day 1 of both treatment periods from 1 h before (first) drug intake until lunch, fluid intake is restricted to the water administered with the drugs, and an additional 240 mL of water at 2 h and 4 h after cocktail administration (mandatory for all subjects).

In all periods total fluid intake on Day 1 is restricted to 3000 mL from lunch until 24 h post-dose. From 24 h – 48 h post-dose (in-house confinement) the total fluid intake is restricted to 4000 mL. The term “post-dose” refers to the cocktail administration in both trial periods.

Green tea, grapefruits, Seville oranges (sour or bitter oranges) and their juices, and dietary supplements and products including St. John's wort (*Hypericum perforatum*) are not permitted starting 7 days before the first study drug administration until last PK sampling of the trial.

Alcoholic beverages are not permitted starting 48 h before the first study drug administration until last PK sampling of the trial.

Methylxanthine-containing drinks or foods (such as coffee, white or black tea, cola, energy drinks, and chocolate) are not allowed from 12 h before administration of trial medication until subsequent discharge from the study site.

Smoking is not allowed during in-house confinement at the trial site.

Excessive physical activity (such as competitive sport) should be avoided starting 7 days before the first administration of trial medication until the end of trial examination.

Direct exposure to the sun or exposure to solarium radiation, treatment with ultraviolet light (e.g. PUVA), or medication with known phototoxicity potential (e.g. doxycycline) should be avoided from the first administration of BI 730357 until the EoTrial examination. The use of sunscreens is mandatory during that time.

If female subjects of child-bearing potential are included, adequate contraception is to be maintained throughout the course of the trial (see Section [3.3.2](#) for adequate measures).

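### Pre-cocktail fluid on Day 1 is not matched between periods: Test has a scheduled 240 mL of water at −1 h that Reference lacks, and its fluid restriction starts an hour earlier

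*Protocol*

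**What the plan says.** **Water with each product.** Section 4.1.4 has medication given "together with about 240 mL of water (BI 730357) or 280 ml (for the cocktail"). In Test, "on Day 1 the morning dose is given 1 h prior to the cocktail". The Test flow chart places BI 730357 at −1:00 and the cocktail at 0:00. The Reference flow chart has nothing between breakfast at −1:30 and the cocktail at 0:00.

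**Restriction before lunch.** Section 4.2.2.2: "On Day 1 of both treatment periods from 1 h before (first) drug intake until lunch, fluid intake is restricted to the water administered" at each dosing. The only other fluid allowed in that window is "an additional 240 mL of water at 2 h and 4 h after cocktail administration".

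**After lunch.** The rule is the same for both periods: "In all periods total fluid intake on Day 1 is restricted to 3000 mL from lunch until 24 h post-dose".

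**What is deliberately matched.** Section 4.1.4 gives the aim and the measure: "To assure comparable conditions for the cocktail administration, the standardised meal will be served also in the Reference treatment". The meal is at −1:30 in both flow charts. No matching water is stated.

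**Design and model.** Reference always comes before Test (section 4.1.4). The model in section 7.3.1 has a random subject effect and a fixed treatment effect. Section 3.2 defends the fixed sequence only on the ground that non-specific time effects are unlikely.

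**The concern.** The protocol accepts that conditions at cocktail dosing should be alike in the two periods, and adds a meal to Reference for that purpose. It does not do the same for the water that Test subjects drink half an hour after that meal is served. It also ties the fluid restriction to an event that occurs at a different time in each period.

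In a randomised crossover, such a difference would still travel with treatment. Here the sequence is fixed as well, so nothing in the data can separate a fluid effect from a drug effect: both change at the same moment in every subject. More subjects would only estimate the combined effect more precisely.

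The place to look would be early absorption. Cmax is a primary endpoint for all four probes, and furosemide is an oral solution with tmax at about 1 h (section 1.2.5). Because section 7.2 sets no acceptance range, a modest ratio will be read at face value. A ratio close to 1 is where a small unmatched condition could matter.

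**Working it through.** **1. Scheduled water on Day 1** (volumes from sections 4.1.4 and 4.2.2.2, times from the flow charts)

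| Time relative to cocktail | Test | Reference |
|---|---|---|
| −1:00, with BI 730357 | 240 mL | none |
| 0:00, with cocktail | 280 mL | 280 mL |
| 2:00 | 240 mL | 240 mL |
| 4:00 | 240 mL | 240 mL |

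- Up to just before 2 h: 240 + 280 = 520 mL against 280 mL; 520/280 = 1.86.
- Up to and including 4 h: 1000 mL against 760 mL; 1000/760 = 1.32.
- Adding the 3000 mL ceiling from lunch to 24 h: 4000 mL against 3760 mL; 4000/3760 = 1.06.

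The absolute gap is 240 mL throughout. The percentage depends on the window chosen.

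**2. Start of the restriction.** The first drug on Day 1 is BI 730357 (−1:00) in Test and the cocktail (0:00) in Reference. One hour earlier gives −2:00 and −1:00. Breakfast at −1:30 is inside the window in Test and outside it in Reference. These start times are derived; the protocol does not print them.

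**3. Net difference from −2 h.** Let v be the volume a Reference subject drinks between −2:00 and −1:00. Test minus Reference is then 240 − v mL. It is positive for v below 240, zero at 240 and negative above. The documents give no v.

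**4. Effect on the estimate.** If the fluid difference multiplies exposure by f, the expected estimate is (true T/R) × f. With fluid condition, period and treatment coinciding, f cannot be estimated.

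**5. Precision.** Table 7.7: 1 was reproduced first, with N = 15 and gCV 30%:

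- σ_W = √ln(1 + 0.30²) = 0.2936
- ω = t(0.95; 14) × σ_W × √(2/15) × √(χ²(0.95; 14)/14) = 1.7613 × 0.2936 × 0.3651 × 1.3007 = 0.2456
- exp(ω) = 1.28; limits around 100% are 78.23 and 127.83, as printed.

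All twelve rows reproduce. None involves fluid, so matching the water changes none of them.

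**6. Illustration only.** The documents give no f. The table assumes shifts in both directions, at gCV 30% and a true ratio of 100%. Coverage comes from a noncentral t with 14 df and noncentrality ln(f)/(σ_W√(2/15)).

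| Assumed f | Illustrative 90% CI | Coverage of true ratio (nominal 90%) |
|---|---|---|
| 0.90 | 70.40 to 115.05 | 75.6% |
| 0.95 | 74.31 to 121.44 | 86.5% |
| 1.00 | 78.23 to 127.83 | 90% |
| 1.05 | 82.14 to 134.23 | 86.8% |
| 1.10 | 86.05 to 140.62 | 78.1% |

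The table shows what a shift would do, not that one exists.

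**The case against.** The strongest reply is that nothing in the documents shows 240 mL of water an hour before dosing to change the exposure of any of the four probes. The meal and the 280 mL taken with the cocktail are already matched, as is every fluid rule afterwards. Metformin peaks at about 2.5 h and rosuvastatin at about 5 h (sections 1.2.4 and 1.2.2), well after the unmatched hour. The post-lunch figure is a ceiling, so permitted intake can differ between periods by far more than 240 mL. The trial is exploratory, and the inhibitor effects cited in section 1.4.2.3 include about 3-fold for digoxin and furosemide AUC and 5-fold for rosuvastatin AUC. A few per cent would be lost beside these.

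Most of that stands, and it limits the point to a small one. A several-fold interaction would hide any fluid effect; a ratio near 1 would not. For metformin, the cited cimetidine effect is itself only 46% on AUC.

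A reader might infer that every subject carries the same imbalance in the same direction. The documents do not support that: the earlier restriction in Test works against its extra water, and the Reference volume before −1 h is unstated. Nor does 520 against 280 mL measure the difference in intake. It counts scheduled water only, over the window where the ratio is largest.

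Breakfast fluid is also uncertain. The described meal lists no drink, and subjects in house may drink only what staff provide. Some administration and design text is redacted or appears incomplete in the public version, so silence on fluid should be read with care.

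What remains is that the stated conditions differ, the printed text gives no reason, and no analysis can correct for it.

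**Conclusion.** The point holds as an unmatched dosing condition. Scheduled water up to and including 4 h differs by 240 mL (1000 against 760 mL, +32%), and the restriction starts one hour earlier in Test. The second part rests on reading the first drug intake as BI 730357 in Test and the cocktail in Reference, which the flow charts support.

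Net fluid before the cocktail could be higher, equal or lower in Test. The size and sign of any pharmacokinetic effect are unknown, and the effect is probably small. It would be wrong to conclude that the T/R ratios are biased, or biased upward by some stated percentage. The supportable statement is that, if fluid has an effect, the fixed sequence and the subject-plus-treatment model assign all of it to BI 730357. Sample size and planned precision are untouched. This is an inexpensive improvement, not a threat to the trial's main conclusions.

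**What to change.** Extend to water what section 4.1.4 does for the meal:

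1. Add one line to the Reference flow chart: 240 mL of plain water at −1:00.
2. Reword section 4.2.2.2 so that the Day 1 restriction starts at a fixed time relative to the cocktail, the same in both periods. A start at −2:00 would leave Test unchanged and put the −1:30 breakfast inside the window in both. If a drink is served with breakfast, state one volume for both periods.

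Scheduled water to 4 h would then be 1000 mL in each period. The cost is one extra glass of water per subject in Period 1, one flow-chart line and one reworded sentence. No drug dose, sample size, model or row of Table 7.7: 1 changes. If Period 1 has already been run, the change can no longer help; the report should state the difference and bear it in mind when reading ratios close to 1.

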4.1.5 Blinding and procedures for unblinding

This Phase I trial will be handled in an open fashion throughout (that is, during the conduct, including data cleaning and preparation of the analysis). This is considered acceptable because the potential for bias seems to be low and does not outweigh practical considerations.

Emergency envelopes will not be provided, because the dose of trial medication is known to investigators and subjects.

PK samples will be labelled in such a way that treatment allocation cannot be derived by the analytical site.

4.1.6 Packaging, labelling, and re-supply

BI 730357

BI 730357 tablets will be provided by BI. They will be packaged and labelled in accordance with local law and the principles of Good Manufacturing Practice. For details of packing and the description of the label, refer to the ISF.

The telephone number of the sponsor and the name, address and telephone number of the trial site are provided in the subject information form. The EudraCT number is indicated on the title page of this protocol as well as on the subject information and informed consent forms.

No re-supply is planned.

Rosuvastatin, digoxin, metformin and furosemide

Rosuvastatin, digoxin, metformin and furosemide will be obtained by the clinical trial site from a public pharmacy. The drug will be dispensed out of the original, unmodified packages.

4.1.7 Storage conditions

Drug supplies will be kept in their original packaging and in a secure limited access storage area in accordance with the recommended (labelled) storage conditions. If necessary, a temperature log must be maintained to make certain that the drug supplies are stored at the correct temperature. If the storage conditions are found to be outside the specified range, the local clinical monitor (as provided in the list of contacts) is to be contacted immediately.

4.1.8 Drug accountability

The investigator or designee will receive the investigational drugs delivered from the sponsor following requirements are fulfilled:

- Approval of the clinical trial protocol by the IRB / ethics committee
- Approval/notification of the regulatory authority, e.g. competent authority
- Availability of the *curriculum vitae* of the Principal Investigator
- Availability of a signed and dated clinical trial protocol

Only authorised personnel documented in the form 'Trial Staff List' may dispense medication to trial subjects. The trial medication must be administered in the manner specified in the CTP.

The investigator or designee must maintain records of the product's delivery to the trial site, the inventory at the site, the use by each subject, and the disposal of unused products. These records will include dates, quantities, batch / serial numbers, expiry ('use-by') dates, and the unique code numbers assigned to the investigational medicinal product and trial subjects. The investigator or designee will maintain records that document adequately that the subjects were provided the doses specified by the CTP and reconcile all investigational medicinal products received from the sponsor. At the time of disposal of remaining trial medication, the investigator or designee must verify that all unused or partially used drug supplies have been returned by the clinical trial subject and that no remaining supplies are in the investigator's possession.

All unused medication will be disposed of locally by the trial site upon written authorisation of the Clinical Trial Leader. Receipt, usage and disposal of trial medication must be documented on the appropriate forms. Account must be given for any discrepancies.

4.2 OTHER TREATMENTS, EMERGENCY PROCEDURES, RESTRICTIONS

4.2.1 Other treatments and emergency procedures

There are no special emergency procedures to be followed. No additional treatment is planned. However, if adverse events require treatment, the investigator can authorise symptomatic therapy. In those cases, subjects will be treated as necessary and, if required, kept under supervision at the trial site or transferred to a hospital until all results of medical evaluations are acceptable.

4.2.2 Restrictions

4.2.2.1 Restrictions regarding concomitant treatment

In principle, no concomitant therapy is allowed except for hormonal contraceptives or ovary hormone replacement. All concomitant or rescue therapies will be recorded (including time of intake on study days) on the appropriate pages of the CRF.

4.2.2.2 Restrictions on diet and life style

While admitted to the trial site, the subjects are restricted from consuming any other foods or drinks than those provided by the staff. Standardised meals will be served at the time points described in the [Flow Chart](#). No food is allowed for at least 4 h after intake of the cocktail.

On Day 1 of both treatment periods from 1 h before (first) drug intake until lunch, fluid intake is restricted to the water administered with the drugs, and an additional 240 mL of water at 2 h and 4 h after cocktail administration (mandatory for all subjects).

In all periods total fluid intake on Day 1 is restricted to 3000 mL from lunch until 24 h post-dose. From 24 h – 48 h post-dose (in-house confinement) the total fluid intake is restricted to 4000 mL. The term “post-dose” refers to the cocktail administration in both trial periods.

Green tea, grapefruits, Seville oranges (sour or bitter oranges) and their juices, and dietary supplements and products including St. John's wort (*Hypericum perforatum*) are not permitted starting 7 days before the first study drug administration until last PK sampling of the trial.

Alcoholic beverages are not permitted starting 48 h before the first study drug administration until last PK sampling of the trial.

Methylxanthine-containing drinks or foods (such as coffee, white or black tea, cola, energy drinks, and chocolate) are not allowed from 12 h before administration of trial medication until subsequent discharge from the study site.

Smoking is not allowed during in-house confinement at the trial site.

Excessive physical activity (such as competitive sport) should be avoided starting 7 days before the first administration of trial medication until the end of trial examination.

Direct exposure to the sun or exposure to solarium radiation, treatment with ultraviolet light (e.g. PUVA), or medication with known phototoxicity potential (e.g. doxycycline) should be avoided from the first administration of BI 730357 until the EoTrial examination. The use of sunscreens is mandatory during that time.

If female subjects of child-bearing potential are included, adequate contraception is to be maintained throughout the course of the trial (see Section [3.3.2](#) for adequate measures).

